Prevention of Postpartum Hemorrhage With Tranexamic Acid
10/27/2023

NCT#03287336

Statistical Analysis Plan

Study Population

This was a prospective, single-center, open-label, dose-ranging study that recruited thirty pregnant women at The George Washington University from February 2018 to May 2019. Inclusion criteria were normal renal function (serum creatinine < 0.9 mg/dL), and greater than 34 +0 weeks gestation age with planned cesarean delivery. Patients were excluded if they had a thromboembolic history or hypersensitivity to TXA (or any antifibrinolytic therapies). The study protocol was approved by the institutional review board (IRB# 041737), and written consent was obtained from each patient before entering the study.

Dosing and Blood Sampling

Thirty patients were treated sequentially: the first ten patients received 5 mg/kg of TXA, the second ten received 10 mg/kg of TXA, and the last ten received 15 mg/kg of TXA. Total body weight was used to calculate the actual doses, which were capped at 1000 mg. TXA (Cyklokapron®) was given intravenously at the time of umbilical cord clamping and was infused via an infusion pump for approximately 15 minutes (500 mL/hour of 110 mL volume).

Maternal blood samples were collected from the opposite arm of drug administration through peripheral venous catheters or separate venous blood draws. Three samples per patient were taken at each sample time, including pre-drug, 10 minutes, 30-60 minutes, 1.5-3 hours, 4-6 hours, 7-8 hours, and 24 hours post end-of-infusion. One of the three samples for PK analysis was drawn into a tube containing potassium ethylenediaminetetraacetic acid (Becton Dickinson Vacutainer tubes, K2 EDTA 7.2 mg). This sample was further centrifuged at 3000 xg for 15 minutes to obtain platelet-poor plasma. The other two samples for PD analysis were drawn into tubes coated with sodium citrate (Becton Dickinson Vacutainer tubes, Na Citrate 0.109 M, 3.2%). Samples were stored on dry ice until further analysis.

Biomarkers and covariates

TXA concentration determined by ultra-high-performance liquid chromatography-tandem mass spectrometry was used as the PK metric. A modified rotational thromboelastometry (ROTEM) analysis⁹ was used to quantify the anti-fibrinolysis effect of TXA. Maximum lysis (ML), the proportion of clot lysed from the maximum clot (range 0-100%), was chosen as the PD marker to

reflect the lysis potential of a formed clot.¹⁰ Briefly, clotting was initiated with tissue factor and recalcification in the presence of exogenous recombinant tissue plasminogen activator, as described.¹¹ The bioanalysis details regarding TXA concentration and ML measurements are published elsewhere.¹¹

Patient-specific routine clinical data were obtained from the electronic medical record. Demographic data included age, height, weight, and BMI. Pre-delivery laboratory data included serum creatinine level (Scr), platelet count, and hematocrit level. Cockcroft-Gault¹² equation was used to estimate creatinine clearance (CrCl). Patient comorbidities (diabetes and hypertension) were also recorded.

Data Analysis

The population approach was adopted using Pumas v1.0.5 (www.pumas.ai).¹³ Non-linear mixed effects modeling with first-order conditional estimation with interaction approach was applied to characterize TXA concentration and its effect on ML. Models were built hierarchically: a base model containing a structural component and a variability component was determined first, followed by the exploration of covariate models to explain the variability in the parameters. The graphic presentation of the data and output was performed using R (version 4.0.2)¹⁴ and ggplot2 (version 3.0.0).¹⁵

Pharmacokinetic modeling

Base model development: One-compartment and two-compartment models with first-order elimination from the central compartment were explored and compared. One-compartment models were parameterized by clearance (CL) and central volume of distribution (Vc). Additional parameters including inter-compartmental clearance (Q) and peripheral volume of distribution (Vt) were used to parametrize the two-compartment models. Between subject variability (BSV) in all the PK parameters was assumed to be log-normally distributed as shown in Equation 1, where P_i denotes the individual parameter, tvP denotes the population typical parameter and η_i denotes the patient-specific deviation from the population parameters that follows a normal distribution with 0 as mean, ω^2 as variance.

$$P_i = tvP \cdot e^{\eta_i} \quad \text{Equation 1}$$

$$\eta_i = (0, \omega^2)$$

Different residual error models were also tested to account for the unexplained residual variability between observations and model predictions, including additive, proportional and combined (both additive and proportional) models. Equation 2 shows the formula of the combined error model. $OBS_{i,j}$ and $IPRED_{i,j}$ are the observation and prediction for the i^{th} patient at time j . The difference between these two variables was characterized by a proportional error term $\varepsilon_{1_{i,j}}$ and an additive error term $\varepsilon_{2_{i,j}}$ that follow normal distributions with mean at 0 and variance at $\sigma_{1\text{or}2}^2$.

$$OBS_{i,j} = IPRED_{i,j} \cdot (1 + \varepsilon_{1_{i,j}}) + \varepsilon_{2_{i,j}} \quad \text{Equation 2}$$

$$\varepsilon_{1\text{or}2_{i,j}} \sim (0, \sigma_{1\text{or}2}^2)$$

Covariate model development: Covariate models were tested to leverage patient-specific covariates to explain the variability in parameters. Potential relationships were assessed from the graphical diagnosis first. Body weight was included in the model using allometric scaling to reflect the impact of organ size on PK. Given the hydrophilic properties of TXA, lean body mass (LBM) calculated by Boer equation¹⁶ was used in the allometry function to compare with total body weight. To explain clearance variability resulting from different levels of kidney functions, kidney function related covariates (Scr, CrCl) were tested upon clearance using a power function.

The final model was chosen based on statistical diagnosis and graphical diagnosis. A model was determined to be significantly better if it reduced the objective function value (OFV) by more than 3.84 units ($P < 0.05$, for 1 degree of freedom). Covariates included in the final model are physiological or mechanistically relevant, and can explain the parameter variability significantly compared to the base model.

Pharmacodynamic modeling

A sequential population approach was used to perform the TXA concentration-ML analysis. This standard approach has been used previously.¹⁷ Briefly, first the PK was developed, and the individual predicted concentrations from the final PK model were used as an independent variable for the PD modeling. Due to the ex vivo characteristics of the ML bioassay, only direct effect models are reasonable. As shown in Equation 3, the PD model was parameterized in terms

of baseline ML (ML_0), maximal fractional inhibition (Imax), concentration of TXA causing 50% of maximal fractional inhibition (IC_{50}), and hill factor (γ). Variabilities of all the parameters were assumed to be log-normally distributed. Different error models were evaluated and compared to account for the random residual variability. The effect of covariates on PD parameters was evaluated in the same manner as for PK parameters.

$$\text{Proportional PD effect model: } E = ML_0 \cdot \left(1 - \frac{Imax \cdot (conc_pred)^\gamma}{IC_{50}^\gamma + conc_pred^\gamma}\right) \quad \text{Equation 3}$$

Model Evaluation

Five-hundred bootstrap samples, each containing 30 patients, were generated by randomly sampling with replacement from the original dataset. Final PK and PD models from previous steps were used to re-estimate the parameters for the 500 bootstrap samples. Subsequently, the 95% confidence interval of the bootstrap results was calculated.

Simulations to derive optimal dosing

In vitro studies have found that 10 mg/L of TXA is required to obtain 80% inhibition of fibrinolysis; thus, 10 mg/L was chosen as the PK therapeutic target.^{18,19} Based on data obtained from women after non-hemorrhagic deliveries, the normal reference of maximum lysis 17% was chosen as the PD therapeutic target.²⁰ Individual TXA concentration and ML were simulated using a dose range of 100-1000 mg. The post-hoc individual parameters from the final PK and PD models were employed for the simulations. The proportion of patients who met the PK or the PD targets were determined for each dosing regimen.

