The study will seek to enroll 45 3rd trimester pregnant women scheduled for non-emergent cesarean section who are at high risk for hemorrhage towards a target of 30 study subjects to conduct a prospective, open-label, dose finding PK study. We will administer three doses of the drug (5 mg/kg, 10 mg/kg and 15 mg/kg) in an escalating fashion by cohort with the lowest dose first. The drug will be administered intravenously at the time of umbilical cord clamping for a non-emergent cesarean section. A maximum of 1 gram will be administered. TXA serum levels at several time points after delivery will be assayed to see if they reach the target plasma concentration of 10 microg/mL. A PK model will be constructed for determining the optimal TXA dose administered at parturition.

Of note, GW currently has an ongoing randomized clinical trial using tranexamic acid to reduce blood loss in surgery for uterine fibroids (IND# 125089). This study is nearly halfway with recruitment and the research coordinator who is helping with this study will also help with the current proposed study.

Plasma sampling: TXA will be administered by intravenous infusion given over 15 minutes using an infusion pump at the time of umbilical cord clamping. Timing of samples will be relative to the end of the infusion intravenous infusion (start of infusion is t=0) and include before receiving

Group	N	TXA Dose
1	10	5 mg/kg
2	10	10 mg/kg*
3	10	15 mg/kg*

the drug, within 10 minutes, 30-60 minutes, 1.5-3 hours, 4-6 hours, 7-8 hours and 24 hours after the drug load. Each volume of blood draw will be approximately 2-5 mL. The first 10 enrolled patients will receive 5 mg/kg, then the second 10 patients will receive 10 mg/kg and the final set of 10 patients will receive 15 mg/kg. Actual times of plasma sampling will be documented. A second IV will be required for participating in the study. Citrated plasma samples will be centrifuged and supernatant will be stored at -70 degree Celsius for further. Breast milk sampling of no more than 2 cc per time point will occur at time points coinciding with maternal feedings.

*max 1 gram dose

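### The PD model assumes each woman's untreated lysis is constant from before delivery to 24 hours after, and the SAP names no test of this, so a postpartum change could be partly absorbed into the TXA parameters

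*SAP*

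**What the plan says.** SAP, Pharmacodynamic modeling, builds the model sequentially: "the individual predicted concentrations from the final PK model were used as an independent variable for the PD modeling". Equation 3 multiplies ML_0 by one minus a sigmoid function of that predicted concentration. Its parameters are given in terms "of baseline ML (ML_0), maximal fractional inhibition (Imax), concentration of TXA causing 50% of maximal fractional inhibition", plus a hill factor. On variability the SAP says: "Variabilities of all the parameters were assumed to be log-normally distributed". ML_0 therefore differs between women, but no change within a woman over time is described.

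On structure the SAP says: "Due to the ex vivo characteristics of the ML bioassay, only direct effect models are reasonable".

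SAP, Dosing and Blood Sampling, states that TXA "was given intravenously at the time of umbilical cord clamping", and protocol section C says the same. Samples were taken at seven times, "including pre-drug, 10 minutes, 30-60 minutes, 1.5-3 hours, 4-6 hours, 7-8 hours, and 24 hours post end-of-infusion". All 30 women received TXA, ten at each of three doses, capped at 1000 mg.

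The covariates listed under Biomarkers and covariates are patient characteristics, comorbidities and pre-delivery laboratory values. Time since delivery is not among them. Model Evaluation consists of a bootstrap of the final models.

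**The concern.** The pre-drug sample is the only one that timing alone guarantees to be drug-free, and it comes before delivery. The other six are taken in the day after delivery and surgery. If lysis without TXA differed between those periods, Equation 3 has only the concentration term with which to describe the difference over time.

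Nothing else named in the plan closes this gap. The direct-effect argument concerns delay between concentration and effect, not the stability of the untreated level. Pre-delivery covariates cannot carry a postpartum change. The bootstrap re-estimates the same model, so it gives intervals around that structure without testing it.

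TXA pharmacodynamics around delivery is a stated aim (protocol section A). The fitted PD model also supplies the proportion of women reaching 17% lysis over 100-1000 mg (SAP, Simulations to derive optimal dosing).

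**Working it through.** The plan gives no figure to reproduce here: no drift, half-life or 24-hour concentration. The check is therefore structural, followed by illustrative simulation.

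**1. Structure.** Equation 3 is E = ML_0 × (1 − Imax·C^γ / (IC50^γ + C^γ)). Only C varies with time. Suppose the true baseline is ML_0 before delivery and ML_0·(1 − d) after. C is zero before and positive after, so a constant-ML_0 fit can mimic the gap by letting inhibition begin at very low C. That means a smaller IC50 and a flatter curve.

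**2. Inputs.**
- From the documents: 30 women, 5, 10 and 15 mg/kg in tens, 1000 mg cap, 15-minute infusion, seven sample times, target 17%.
- Assumed: ML_0 85%, Imax 0.95, IC50 6 mg/L, hill 1.5, residual SD 5 points; two-compartment PK (CL 9, Vc 12, Q 15, Vt 15; variability 25% on CL, 20% on Vc); weight 85 kg (SD 18); window midpoints as sample times. Fits are pooled least squares, not the SAP's mixed model.

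**3. Parameters under a lasting fall, constant-ML_0 fit.**

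| Fall d | IC50 (true 6) | Shift, about | Hill (true 1.5) |
|---|---|---|---|
| 10% | 5.6 | -6% | 1.34 |
| 20% | 5.1 | -14% | 1.15 |
| 30% | 4.2 | -30% | 1.00 |

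The fitted values are rounded, so dividing them can differ from the stated shift by a point. Imax drifts towards 1. With a post-delivery term, IC50 returns to about 6.

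**4. Concentration needed for 17% lysis.** C17 = IC50 × (f / (Imax − f))^(1/γ), with f = 1 − 17/B and B the baseline that applies after delivery.
- d = 10%: B = 76.5, f = 0.778, C17 = 6 × (0.778/0.172)^(2/3) = 16.4 mg/L
- d = 20%: B = 68, f = 0.750, C17 = 6 × (0.750/0.200)^(2/3) = 14.5 mg/L
- d = 30%: B = 59.5, f = 0.714, C17 = 6 × (0.714/0.236)^(2/3) = 12.6 mg/L

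The constant-ML_0 fits exceed these by about 3%, 5% and 8%. A separate run of the same settings gave 16.8, 15.2 and 13.9 mg/L (+2%, +5%, +10%), which shows the simulation spread. The sign is upward: the concentration needed is overstated.

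**5. Target attainment, same settings, at an assumed 1 hour.** At 600 mg the proportion reaching 17% moves by about 5, 15 and 19 points. At 1000 mg it moves by 1 point or less.

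**6. Second set of assumptions.** One compartment, V 25 L, half-life 2 or 3 h, ML_0 80%, Imax 0.9, hill 2, IC50 8 or 2.5, a separate ML_0 per woman.
- No drift: IC50 is recovered (8.05-8.09 and 2.43-2.51).
- Lasting 30% fall: B = 56, f = 0.696, true C17 = 8 × (0.696/0.204)^(1/2) = 14.8, or 4.6 for IC50 2.5. The fits give 16.0 and 16.3 (+8%, +10%), and 4.7 and 4.8 (+2%, +3%).

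**7. Shape and direction.** In the first set, a gradual 6-hour change moves IC50 by 5% or less. In the second, an immediate 30% fall that fades with a time constant of 6 or 12 h takes IC50 from 8 to 6.4-7.0, so the result depends on the assumed shape. A 20% fading rise takes it the other way, to 8.6-8.8, with Imax 0.86-0.87 against 0.90.

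**8. How far the design separates time from drug.** Simulated 24-hour TXA is 0.01-0.03 mg/L in the first set and 0.006-0.135 in the second, which is nearly drug-free if those assumptions hold. The dose groups give different concentrations at the same time, but the cap binds above 1000/15 = 66.7 kg in the top group. At an assumed 88 kg, 10 and 15 mg/kg become 880 and 1000 mg, about 14% apart.

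**The case against.** The strongest objection is that the premise is undocumented. Nothing in either document says that lysis in this assay, run with added plasminogen activator, changes after delivery without TXA. The SAP also selects models by statistical and graphical diagnosis, where a misfit between pre-drug and 24-hour samples could show up. And the quantity that the plan reports, attainment of 17%, is partly protected because the parameter errors offset. All of this stands and limits the point to an untested assumption. It does not answer the point: no check against time is named, and offsetting errors do not protect the reported IC50, Imax and hill factor.

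Three stronger readings are tempting and not supported.

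- A reader might infer that all postpartum change is credited to TXA. It is not: some goes into ML_0 and residual error. With a lasting 30% fall in the second set, fitted ML_0 dropped from 0.80 to 0.67-0.68 in three of four scenarios, and to 0.77 in the fourth.
- A reader might infer that the fit makes the 17% target look easier to reach. That comes from comparing with the pre-delivery baseline: 6 × (0.8/0.15)^(2/3) = 18.3 mg/L, against which 16.8, 15.2 and 13.9 look 8%, 17% and 24% low. Women are treated at delivery, so the post-delivery baseline is the relevant one, and against it the error is small and upward.
- A reader might infer that the TXA effect could be wholly spurious. In the second set, a 30% fall with no drug effect does produce an Imax of 0.30-0.58, but nothing in the documents suggests that TXA has no effect on this assay.

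**Conclusion.** The concern holds as an untested assumption with a cheap remedy. ML_0 is constant within each woman, time since drug coincides with time since delivery, nobody is untreated, and no test of a stable baseline is named. The 24-hour sample and the dose groups could partly separate time from drug, but the model as written does not use them for this.

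The size is conditional. For a lasting fall of 10-30%, IC50 shifts by about -6% to -30%, while the concentration for 17% lysis is overstated by about 3% to 8%. The drift, the PK and PD values and the 24-hour concentrations are all assumed. The simulations use least squares, so they show direction and rough size and do not forecast this trial's estimates. This does not invalidate the PD analysis.

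**What to change.** Using the existing samples:

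1. Test a pre-delivery versus post-delivery factor on ML_0 under the SAP's own rule (OFV drop above 3.84, 1 df). If a two-parameter gradual trend is also tested, use 5.99 (2 df).
2. Confirm from the measured concentrations that 24-hour TXA is near zero, then tabulate observed ML pre-drug against 24 h within women. A change that has faded by 24 h would be missed here, so also plot residuals against time by dose group.
3. If the term is kept, derive the proportion reaching 17% from the post-delivery ML_0 and report how far it moves. If it is not kept, report that a constant baseline was tested.

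The test will not catch every drift. In the second set, a 30% fall lowered −2 log-likelihood by 3.5 to 254 with a two-parameter term, and 3.5 is below 5.99. A null result therefore supports the constant baseline without proving it.

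The cost is one or two more parameters and slightly wider intervals for ML_0 and IC50. The SAP is written in the past tense and dated after recruitment ended, so the added analysis should be labelled as such.

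### Does log-normal variability on Imax and baseline ML, with no stated upper bound, distort the proportion of women meeting the 17% ML target?

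*SAP*

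**What the plan says.** SAP, Pharmacodynamic modeling, Equation 3 gives E = ML0 × (1 − Imax × C^γ / (IC50^γ + C^γ)). Imax is defined there as a fraction. On between-subject variability the section says "Variabilities of all the parameters were assumed to be log-normally distributed". The form is shown under Pharmacokinetic modeling: "Between subject variability (BSV) in all the PK parameters was assumed to be log-normally distributed as shown in Equation 1", that is, a typical value times exp(η), which is positive and has no upper limit.

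Under Biomarkers and covariates, ML is "the proportion of clot lysed from the maximum clot (range 0-100%), was chosen as the PD marker". Under Simulations to derive optimal dosing, "the normal reference of maximum lysis 17% was chosen as the PD therapeutic target"; "The post-hoc individual parameters from the final PK and PD models were employed for the simulations"; and "The proportion of patients who met the PK or the PD targets were determined for each dosing regimen".

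Neither document mentions a cap, a logit transform, a fixed Imax or truncation of predicted ML.

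**The concern.** Two of the four PD parameters have natural ceilings that the stated distribution ignores. If a woman's Imax exceeds 1, Equation 3 predicts negative lysis at high concentration. If her ML0 exceeds 100%, predicted baseline lysis is more than the whole clot.

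The individual estimates go straight into the dose simulations. With the other parameters held fixed, a larger Imax lowers the concentration at which ML reaches 17%, so a woman could be counted as meeting the target at too low a dose. An excessive ML0 acts the other way. Negative ML does not itself alter the count, since it is already below 17%, so any error would sit near the threshold. The PK target of 10 mg/L is untouched. At stake is the PD half of the attainment results for 100 to 1000 mg.

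**Working it through.** The documents state no typical value, variance or attainment result for the PD model, so there is no figure to reproduce. From the SAP come Equation 3, the 17% target (read as E ≤ 17), 30 women, seven sampling times and post-hoc individual parameters. All other inputs are assumptions.

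**1. Can the limits be exceeded?** P(X > bound) = 1 − Φ(ln(bound / typical value) / ω).

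| Parameter | Typical value | ω 0.05 | ω 0.1 | ω 0.2 |
|---|---|---|---|---|
| Imax (bound 1) | 0.80 | 0.0% | 1.3% | 13% |
| | 0.90 | 1.8% | 15% | 30% |
| | 0.95 | 15% | 30% | 40% |
| ML0 (bound 100) | 60 | 0.0% | 0.0% | 0.5% |
| | 80 | 0.0% | 1.3% | 13% |
| | 90 | 1.8% | 15% | 30% |

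So the formal point is right. With ML0 80, Imax 1.1 and saturation 0.95, E = 80 × (1 − 1.045) = −3.6%.

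**2. How far could the threshold move with all else fixed?** C/IC50 = (f / (1 − f))^(1/γ), with f = (1 − 17/ML0) / Imax. For ML0 80 and γ 2, f is 0.7875 at Imax 1.0 and 0.7159 at Imax 1.1. C/IC50 is then 1.925 and 1.587, 18% lower. For ML0 60, γ 2 the drop is 14% (1.590 to 1.367); for ML0 90, γ 1.5 it is 25% (2.642 to 1.990).

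**3. Why "all else fixed" is the wrong comparison.** The simulations use post-hoc estimates, and each woman's Imax, IC50, γ and ML0 are fitted jointly to her own ML values. If Imax is held down, IC50 and γ move so that the curve still follows the data.

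Take ML0 80, γ 1.5, IC50 5 and Imax 1.04. Then f = 0.7875/1.04 = 0.757, C/IC50 = 2.135, and the curve crosses 17% at 5 × 2.135 = 10.7 mg/L. Cutting Imax to 1 alone gives C/IC50 = 2.395 and a crossing at 12.0 mg/L, 12% higher. With Imax at 1 and IC50 at 10.67/2.395 = 4.46, the crossing is back at 10.7 mg/L. That move in IC50 is ln(4.46/5) = −0.11 on the log scale, small beside an assumed ω of 0.5.

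Simulation agrees. Assumptions: ML0 80, IC50 5 (ω 0.5), Hill 1.5, residual SD 5, log-normal truth, typical Imax 0.90 to 0.95 with ω 0.1 to 0.2, 300 women per scenario, population values treated as known. Among women with post-hoc Imax above 1, the median was only 1.02 to 1.04. Capping after the fit raised the concentration needed by a median of 4 to 11%. Re-estimating with Imax at or below 1 changed it by 0.2% or less.

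A second check of eight scenarios also held ML0 at or below 100. The median change on re-estimation was at most 0.4%, against 2 to 9% for the cap, and attainment at 10 mg/L did not change. The exact zero depends on the assumed values; read it as no visible effect.

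**4. Effect on the attainment count, with population parameters re-estimated.** One woman is 1/30 = 3.3 points.

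- Log-normal truth (so some women truly have Imax above 1) and capping after the fit, 27 scenarios: post-hoc Imax above 1 in 0 to 31% of women, ML0 above 100 in 0 to 3%. Mean excess at 10 mg/L is 0 to 2.2 points, and 6.8 points (about 2 of 30 women) at the 95th percentile of trials. At 40 mg/L the mean excess is at most 0.2 points.
- Bounded truth, log-normal fit, 18 scenarios: Imax above 1 in 0 to 1.4% of women, excess at most 0.2 points.

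If a fraction above 1 is impossible, the second case is the relevant one.

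**The case for a change.** The strongest reply is that the choice of distribution moves the results even if the bound itself does not. Fitted to the same bounded-truth data, log-normal minus logit-normal attainment ranged from −5.8 to +0.2 points at 10 mg/L and from +3.4 to +12.6 points at 40 mg/L. A separate comparison with population values treated as known gave mostly 0 to 3 points, with extremes of −9 and +7. Several of these exceed one woman.

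The differences are real, but they do not come from values beyond the limits. They are largest at 40 mg/L, where capping Imax changes attainment by at most 0.2 points on average. They reflect the shape of the two distributions, and neither was consistently nearer the truth. The two extremes show this:

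- Typical Imax 0.90, ML0 95, ω 0.2, residual SD 10, at 5 mg/L: log-normal 5.6%, bounded 14.2%, truth 14.7%. The bounded form is nearer.
- Typical Imax 0.95, ML0 80, ω 0.1, residual SD 10, at 30 mg/L: log-normal 70.9%, bounded 63.8%, truth 69.3%. The log-normal form is nearer, although the data were generated from the bounded one.

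It can also be said that the SAP should have stated how Imax was handled. That stands as a point of completeness. But Data Analysis says the variability component was settled during base-model building, so variability on Imax may not have been kept. For ML0, the pre-drug sample in Dosing and Blood Sampling ties each woman's baseline to an observed value within 0 to 100%.

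**Conclusion.** The wording does permit out-of-range individual values, but no material effect on PD target attainment is shown. With a true Imax within its limit, the excess is at most 0.2 points, about one-sixteenth of a woman (0.2/3.3). The larger figures need simulated women with an impossible Imax, a cap applied after the fit, or both. Replacing log-normal by logit-normal would exchange one conventional form for another with no demonstrated gain in accuracy, and with 30 women a logit-normal Imax may itself be poorly estimated. The SAP is also written in the past tense, so substituting a different distribution would misdescribe the analysis it reports.

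This rests on assumed PD values throughout (typical Imax 0.80 to 0.95, ML0 60 to 95, ω for Imax 0.05 to 0.2, residual SD 5 or 10) and, for the individual re-estimation, on population values treated as known. Whether any of the 30 women had a post-hoc Imax above 1 cannot be learned from the documents. A count of such values would be a helpful line in a report, but the plan does not need to change.
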